Rigorous, randomized, placebo-controlled trials are necessary to determine whether lowdose testosterone augmentation will be an effective treatment for depression in women with inadequate response to antidepressant **therapy**. In this application, a double-blind, placebocontrolled trial of adjunctive low-dose testosterone for inadequate response to antidepressant **therapy** among MDD women is proposed.

*Specific Aim 1*. Low-dose testosterone augmentation improves depressive symptoms in women with MDD and partial/nonresponse to antidepressant therapy.

*Aim 1A.* We will investigate in female antidepressant therapy partial/nonresponders whether low-dose testosterone augmentation for 8 weeks leads to a significantly greater reduction in depressive symptoms than placebo.

*Aim 1B.* We will investigate whether a key mechanism underlying the effects of testosterone administration on depressive symptoms is an increase in neuroactive testosterone metabolites, including 3alpha-diol.

*Specific Aim 2.* Adjunctive low-dose testosterone is safe and well-tolerated in women with MDD and partial/nonresponse to antidepressant therapy. We will investigate whether low-dose testosterone augmentation therapy for 8 weeks is safe and well-tolerated in female antidepressant therapy partial/non-responders compared to placebo.

*Specific Aim 3.* Low-dose testosterone augmentation improves two specific RDoC construct symptoms (in the Arousal/Physiologic Processes Domain) in women: fatigue and sexual dysfunction. We will investigate in female antidepressant therapy partial/nonresponders whether low-dose testosterone augmentation for 8 weeks improves associated fatigue and sexual dysfunction compared to placebo.

*Specific Aim 4.* Low-dose testosterone therapy in women with treatment resistant depression will cause functional changes in the brain. We will investigate the mechanisms and functional neuroanatomy of the effects of testosterone on different regions of the brain in women with treatment resistant depression. This will serve as preliminary data for future studies and grants.

*Exploratory Aim:* We will investigate androgen and other hormonal correlates of functional and structural neuroanatomy in women with treatment resistant depression compared with healthy, non-depressed controls. This will serve as preliminary data for future studies.

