# Baseline Visit for the Randomized, Placebo-Controlled, Augmentation Study: Eligible

subjects will undergo baseline testing immediately before the augmentation phase of the protocol. Baseline visit testing will include the following. However, the blood draw will not be repeated if the Baseline visit occurs within 2 weeks of the screening visit.

- Weight, vital signs, waist-to-hip ratio, and consumptive habits (alcohol, caffeinated beverages) will be recorded
- Urine pregnancy test (for premenopausal women only). Postmenopausal is defined as at least one year since last menses and FSH in the postmenopausal range
- Baseline endocrine blood testing: free testosterone, estradiol, neuroactive steroid panel, DHEAS, blood cortisol, late night salivary cortisol and 8 a.m. salivary cortisol
- o Baseline safety blood testing: ALT, creatinine, CBC
- Depression: MADRS, IDS-SR, CGI-I, S
- Cognitive Functioning: CPFQ
- o Persistent/residual symptom assessment: SF-36, BFI, ESS, FSS, DISF
- Safety assessments: SAFTEE-SI, CHRT, and hirsutism and skin assessments
- We will distribute the Study Drug Compliance and Hot Flash Diary or Menopausal Symptom Diary

• We will also collect DNA to be banked for a future exploratory study into whether androgen receptor CAG repeat length moderates androgen-behavior relationships (based on data by Seidmanet *et al.*).

**Follow-up Visits (Placebo-Controlled Augmentation Phase):** Subjects will then be randomized to receive low-dose testosterone or placebo. Follow-up visits will take place at weeks 2, 4, 6 and 8 post-baseline. Follow up visits will include:

- Urine pregnancy test (for premenopausal women only). Postmenopausal is defined as at least one year since last menses and FSH in the postmenopausal range (weeks 2, 4, 6 and 8)
- Free testosterone levels (weeks 2, 4, 6 and 8)
- Skin evaluations to monitor for side effects (weeks 4 and 8)
- Weight and vital signs will be recorded (weeks 4 and 8)
- Waist-to-hip ratio (week 8)
- Depression: MADRS, IDS-SR, CGI-I, S (weeks 2, 4, 6 and 8)
- Cognitive Functioning: CPFQ (weeks 2, 4, 6 and 8)
- Persistent/residual symptom assessment: SF-36, BFI, ESS, FSS, DISF (weeks 2, 4, 6 and 8)
- Safety: SAFTEE-SI, CHRT (weeks 2, 4, 6 and 8)
- Estradiol levels (weeks 2, 4, 6 and 8)
- Salivary cortisol (week 8)
- Medication management sessions (weeks 2, 4, 6 and 8)
- Neuroactive steroid panel (week 8)

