Testosterone Antidepressant Augmentation in Women

NCT01783574

Version Date: February 1, 2017

Study Endpoints and Data Analysis

Specific Aim 1: We will investigate in women with partial/nonresponse to antidepressant therapy whether low-dose testosterone augmentation leads to a significantly greater reduction in depressive symptoms compared to a placebo group over an 8-week period.

Experimental Strategy and Endpoints: To investigate the effects of physiologic testosterone augmentation on antidepressant therapy partial/nonresponse, 50 women with partial/nonresponse to antidepressant therapy randomized to testosterone augmentation and 50 to placebo in the 8-week randomized, double-blind placebo controlled study delineated in the "Overall Protocol", will be compared. Depressive symptom endpoints will be measured at baseline and weeks 2, 4, 6 and 8. The primary endpoint will be MADRS score in weeks 2-8.

• These data will determine the effects of low-dose testosterone augmentation on depressive symptoms in women with partial/nonresponse to antidepressant therapy.

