Data Analysis: For Aim 1, the data will be analyzed using a mixed-effect linear regression model. The randomization will be stratified by site, estrogen use, and one vs. more than one adequate antidepressant therapy trial. The model will specify a baseline MADRS score and baseline non-responder vs. partial responder as covariates and then an "on treatment score," which is the score from weeks 2 through 8. The following will be entered into the model as covariates: baseline non-responder vs. partial responder, one vs. more than one adequate antidepressant therapy trial, baseline free testosterone level, baseline age and site (MGH or Butler Hospital). The on treatment score will have a fixed treatment effect and a random patient effect. We will examine interactions between menopausal status and effect to determine whether menopausal status moderates the treatment effect. This model is the same as in a repeated measures analysis of (co)variance with the assumption of compound symmetry. Our pilot data shown in Figure 2 fits this model. Specifically, based on our preliminary data, we expect a rapid improvement in depression severity by 2 weeks followed by maintenance of the effect of the subsequent 6 weeks. One advantage of this method is that it allows us to use data from patients who drop out early despite our plans to obtain follow-up data on all patients randomized and analyze all data obtained. A subject who drops out in the middle of the study will add data to the analysis. The drop-out rate should be low due to the relatively short duration of the study and the anticipated low side effect profile, the latter as confirmed in our pilot study in this population in which we had no drop-outs over the 8-week period. This model assumes that the drop-outs are missing at random. We will attempt to obtain 8-week observations on all patients, including drop-outs. Sensitivity analysis will be performed to determine whether our conclusions are sensitive to this assumption (185). Secondary analyses will determine whether the response of depressive symptoms to testosterone is affected by baseline androgens and neuroactive metabolites (including free testosterone level, DHEAS, and 3α -diol), estradiol, blood cortisol, late night cortisol and 8 a.m. salivary cortisol, and changes in the same variables over the 8-week period. Pre-treatment free testosterone level will be entered into the model as a covariate along with a treatment baseline interaction. Other covariates that will be explored will be age, menopausal status, baseline MADRS score, change in estradiol levels, change in free testosterone levels and BMI. As a secondary

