
endpoint, we will determine the 8-week remission rate in an exploratory analysis. Remission will be defined as MADRS score<10. Comparison of ratios of remitters to the total number of study participants in the testosterone and placebo groups will be compared using a Fisher Exact test. Another secondary endpoint will be effects of testosterone on functional measures. The same methods as described for MADRS score analyses will be used to analyze functional measures, including the SF-36.

For Aim 1B, the primary analysis will be to determine whether the neuroactive metabolite of testosterone, 3a-diol, is an important determinant of the effects of testosterone on our primary endpoint, MADRS score. We expect to be able to distinguish the effect of 3a-diol from the effect of an increase in serum free testosterone levels because we expect the relative levels of the two hormones will differ, i.e. we expect that some study subjects will convert a greater proportion of testosterone to the 3α -diol metabolite than other study subjects. Analyzing the effect of both free testosterone and 3α-diol on the outcome (MADRS score) by linear regression, we hope to determine the relative importance of each hormone as a determinant of outcome. It is conceivable that both will correlate with the MADRS score, simply reflecting absorption of testosterone, and it is also possible that one will correlate with MADRS score, and the other will not. For instance, if the coefficient of the metabolite 3α -diol in a regression of outcome on 3α-diol and free testosterone is large while that of free testosterone is small, then we would conclude that the active factor is 3a-diol rather than free testosterone. If the correlation coefficient between the two of these is large, we would not have data to make a determination of which is active.

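### The Aim 1B regression names only two hormones as regressors, so pre-existing differences between women, or an arm effect by another route, can be read as mechanism

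*SAP*

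**What the plan says.** The protocol's Specific Aims frame Aim 1B as a question about change: whether a key mechanism "is an increase in neuroactive testosterone metabolites, including 3alpha-diol".

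The SAP (Specific Aim 1, Data Analysis, Aim 1B paragraph) makes the primary analysis a test of whether 3α-diol "is an important determinant of the effects of testosterone on our primary endpoint, MADRS score". The method for the two hormones reads: "on the outcome (MADRS score) by linear regression, we hope to determine the relative importance of each hormone as a determinant of outcome". The decision rule is that if the 3α-diol coefficient in a model with that metabolite "and free testosterone is large while that of free testosterone is small, then we would conclude that the active factor is" the metabolite. If the two hormones are highly correlated, no determination would be made.

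The paragraph does not say which visit's MADRS is the outcome, or whether the hormones enter as levels or changes. It names no baseline value and no arm term. For Aim 1 itself, "the data will be analyzed using a mixed-effect linear regression model", with baseline MADRS, baseline free testosterone, treatment and a random patient effect. The functional measures and Aim 3 refer back to that model; Aim 1B does not.

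The protocol's baseline visit lists "Baseline endocrine blood testing: free testosterone, estradiol, neuroactive steroid panel, DHEAS". On treatment, free testosterone is drawn at weeks 2, 4, 6 and 8, but the neuroactive panel only at week 8.

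**The concern.** Randomisation balances the arms. It does not balance women with high and low 3α-diol. A woman's week-8 level reflects where she started as well as what treatment did, and her week-8 MADRS partly reflects her baseline MADRS. If the two baselines are related, a regression on the two hormones alone finds an association even when no change on treatment mattered.

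The absence of arm opens a second route. If testosterone acts on mood through something other than these two measurements, both hormones still mark who was treated, and their coefficients pick up that effect.

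At stake is the sub-aim's conclusion about which hormone is active, which would feed into later work. The primary efficacy comparison is not affected.

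**Working it through.** The documents give no significance level, power, SD or correlation for Aim 1B, so there is no planned figure to reproduce. From the documents: 50 + 50 women, and one on-treatment 3α-diol value each. Everything else below is assumed: two-sided 5%, SD units, and no effect of either hormone on MADRS.

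**1. Baseline confounding, one score per woman, n = 100**

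Assumptions:
- baseline 3α-diol correlates c with baseline MADRS and 0.5 with baseline free testosterone;
- baseline MADRS correlates 0.5 with week-8 MADRS;
- treatment raises free testosterone by A (mean 1, SD 0.4; zero on placebo) and 3α-diol by 0.8A;
- added noise has SD 0.3 for free testosterone and 0.5 for 3α-diol.

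Then:
- Var(A) = 0.5 × (1 + 0.16) - 0.25 = 0.33
- Var(3α-diol) = 1 + 0.64 × 0.33 + 0.25 = 1.461
- Var(free T) = 1 + 0.33 + 0.09 = 1.42
- Cov(3α-diol, free T) = 0.5 + 0.8 × 0.33 = 0.764
- determinant = 1.461 × 1.42 - 0.764² = 1.491
- covariances with MADRS: 0.5c for 3α-diol and 0.25c for free T
- spurious 3α-diol coefficient = (1.42 × 0.5c - 0.764 × 0.25c) / 1.491 = 0.348c
- SE ≈ √(1.42 / 1.491 / 100) = 0.098, falling to about 0.096 at c = -0.5
- false-positive rate = Φ(-1.96 + z) + Φ(-1.96 - z), with z = |coefficient| / SE

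| c | coefficient | z | by formula | simulated (2,000 trials) |
|---|---|---|---|---|
| 0 | 0 | 0 | 5% | 5-6% |
| -0.2 | -0.070 | 0.72 | 11% | 10-11% |
| -0.3 | -0.104 | 1.08 | 19% | 18% |
| -0.4 | -0.139 | 1.45 | 30% | not run |
| -0.5 | -0.174 | 1.82 | 45% | 44-45% |

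Adding baseline MADRS and both baseline hormones brought the simulated rate to 4-6% throughout. Other nuisance assumptions at n = 100 gave 7-12% at -0.2 and 17-32% at -0.4. A larger treatment-induced rise dilutes the problem: at c = -0.4, one such set fell from 30% with no rise to 25%, 22% and 19% with rises of 1, 2 and 3 SD in both hormones.

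**2. Arm effect by another route**

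Take c = 0 and a 0.5 SD benefit of treatment carried by neither hormone. After adjustment for the three baselines but not arm:
- variances of the two changes: 0.64 × 0.33 + 0.25 = 0.461 (3α-diol) and 0.33 + 0.09 = 0.42 (free T); covariance 0.8 × 0.33 = 0.264
- determinant = 0.461 × 0.42 - 0.264² = 0.124
- covariances with MADRS: -0.5 × 0.8 × 0.25 = -0.100 and -0.5 × 0.25 = -0.125
- 3α-diol coefficient = (0.42 × -0.100 + 0.264 × 0.125) / 0.124 = -0.07
- free T coefficient = (0.461 × -0.125 + 0.264 × 0.100) / 0.124 = -0.25

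Both should be zero. The simulated false-positive rate for 3α-diol was 7.6% without arm and 5.4% with it. Under another set of assumptions it was 15-18% without arm and about 5% with it. Baselines alone are therefore not enough.

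**3. Repeated scores, only if weeks 2-8 are entered as separate rows**

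Four scores against one 3α-diol value give a design effect of 1 + 3ρ. At ρ = 0.3, 0.5, 0.7 and 0.8 the SE is too small by √1.9 = 1.38, √2.5 = 1.58, √3.1 = 1.76 and √3.4 = 1.84, and a nominal 5% becomes 15.5%, 21.5%, 26.6% and 28.8%. With one row per woman the design effect is 1.

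**The case against.** The strongest reply is that a short paragraph is being read as a full specification. Aim 1B sits within Aim 1, whose model has baseline MADRS and a patient effect. The paragraph also speaks of an increase in free testosterone, so changes may be intended. The SAP plans secondary analyses of baseline hormones and their eight-week changes, and lists baseline MADRS among covariates to explore. The wording is tentative, and there is a stated no-conclusion rule for highly correlated hormones.

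Part of this stands: level versus change is not settled by the text. But Aim 1B names its own regression and its own decision rule, without the back-reference used elsewhere. The secondary analyses do not alter that primary analysis, and none is said to override its conclusion.

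A reader might infer that the error bars will be far too narrow. The endpoint sentence, "The primary endpoint will be MADRS score in weeks 2-8", together with a linear regression that names no patient effect, invites this. The documents do not support it as a finding. Nothing says that four scores will be stacked, and a single on-treatment 3α-diol value makes one row per woman the more natural reading, for which ordinary standard errors need no clustering correction.

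A reader might also infer that every baseline value will be in hand. The protocol does not repeat the baseline blood draw when that visit falls within 2 weeks of screening. It schedules the visit at about 1-2 weeks, and its screening bloods include free testosterone but no neuroactive panel.

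**Conclusion.** The concern holds for the missing baselines and the missing arm term. Followed as written, the Aim 1B regression can name an active hormone on the strength of pre-treatment differences or of a treatment effect by another route. With 100 women and one score each, the false-positive rate for 3α-diol is roughly 7-30% at assumed baseline correlations of -0.2 to -0.4. At zero correlation baseline confounding vanishes, leaving only the arm route. These figures also depend on the assumed persistence of hormones and MADRS and on the size of the hormone rise.

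The standard-error problem is conditional: about 1.4 to 1.8 times too small at within-woman correlations of 0.3-0.8, and only if repeated scores are entered without a patient effect. The point should be fixed before analysis, but it concerns a mechanistic sub-aim and not the efficacy result.

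**What to change.** Rewrite the Aim 1B paragraph to specify:

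1. Outcome: one score per woman, week-8 MADRS, matching the only on-treatment 3α-diol value.
2. Regressors: week-8 3α-diol and week-8 free testosterone.
3. Covariates: baseline MADRS, baseline 3α-diol, baseline free testosterone and treatment arm. With its baseline in the model, each hormone coefficient refers to change, as Aim 1B intends.
4. If weeks 2-8 scores are used as repeated rows instead, add the Aim 1 random patient effect, and acknowledge that a week-8 hormone value would then be explaining earlier scores.
5. Missing baseline 3α-diol: confirm that the panel is drawn before treatment in every woman, or state how those without it are handled. Adjust for baseline MADRS and arm in all women regardless. In simulations where confounding ran only through baseline MADRS, that covariate alone restored about 5%.

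The cost is four degrees of freedom and some precision. Under the assumptions of step 1, the large-sample SE of the 3α-diol coefficient rises from about 0.10 to √(0.75 × 0.42 / 0.124 / 100) = 0.16 with the three baselines, where 0.75 = 1 - 0.5² is the residual variance. Adding arm leaves it at about 0.16, since √(0.75 × 0.17 / 0.0471 / 100) = 0.165. Here the within-arm Var(A) is 0.5 × 0.16 = 0.08, the change variances are 0.64 × 0.08 + 0.25 = 0.301 and 0.08 + 0.09 = 0.17, and the determinant is 0.301 × 0.17 - 0.064² = 0.0471. The narrower interval came from between-woman differences that say nothing about an increase. Even so adjusted, the coefficients remain observational, and the SAP should word its conclusion accordingly.

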Specific Aim 2: We will investigate in women with partial/nonresponse to antidepressant therapy whether adjunctive low-dose testosterone is safe and welltolerated in women with partial/nonresponse to antidepressant therapy. Experimental Strategy and Endpoints: To investigate whether adjunctive physiologic testosterone is safe and well-tolerated over the 8-week protocol, we will compare rates of adverse events in subjects randomized to testosterone augmentation to those receiving placebo using the SAFTEE-SI. These endpoints will also include increases in ALT and hirsutism and skin assessment scores and decreases in HDL cholesterol. The primary endpoint will be adverse effect rate.

• These data will determine whether adjunctive physiologic testosterone is safe and well-tolerated in women with relative partial/nonresponse to antidepressant therapy.

Data Analysis: Rates for each adverse effect will be computed by group. Differences between treatment groups in dropout rates will be examined using a Fisher's Exact test, though every effort will be made to retain subjects through the 8-week course. If a trend (p < .10) indicative of differential dropout is detected, a more detailed survival analysis will be completed to illustrate the timing and magnitude of these differences.

Specific Aim 3: Low-dose testosterone augmentation improves persistent/residual symptoms in women with antidepressant-resistant depression.

Experimental Strategy and Endpoints: To investigate the effects of low-dose testosterone augmentation on fatigue and energy in women with antidepressant-resistant depression, the 50 women with antidepressant-resistant depression

randomized to testosterone augmentation and 50 to the placebo arm of the 8-week randomized, double-blind placebo controlled study delineated in the "Overall Protocol", will be compared. Energy/fatigue and sexual function/libido endpoints will be measured at baseline and weeks 2, 4, 6 and 8. The primary endpoint will be BFI score weeks 2-8.

• These data will determine the effects of low-dose testosterone augmentation on fatigue and sexual function in women with antidepressant-resistant depression.

Data Analysis: The data will be analyzed using a mixed-effect linear regression model, using methods and assumptions as in Specific Aim 1 Data Analysis, above.

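### Aim 1B would name 3alpha-diol the active factor by setting a large coefficient against a small one, with no common scale, no test of the difference and no correlation cut-off

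*SAP*

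**What the plan says.** The Aim 1B analysis is described only in the SAP, in the Aim 1B paragraph under Specific Aim 1, which calls it a primary analysis. It takes both hormones' effects "on the outcome (MADRS score) by linear regression, we hope to determine the relative importance of each hormone as a determinant of outcome". As an example, it says that if the 3alpha-diol coefficient "is large while that of free testosterone is small, then we would conclude that the active factor is 3a-diol rather than free testosterone". This is introduced as an instance, but it is the only rule given for choosing between the hormones. One safeguard follows: "If the correlation coefficient between the two of these is large, we would not have data to make a determination of which is active".

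The paragraph expects the two hormones to be separable because "some study subjects will convert a greater proportion of testosterone to the" metabolite than others. It also allows that both may track MADRS, "simply reflecting absorption of testosterone, and it is also possible that one will correlate with MADRS score, and the other will not".

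It does not state which women enter, which MADRS visit is used, whether treatment arm or baseline MADRS is in the model, the hormone scale, what counts as large or small, any test of the difference, or the correlation that stops the inference. The protocol (Follow-up Visits) schedules the neuroactive steroid panel on treatment at week 8 only, whereas MADRS and free testosterone are measured at weeks 2, 4, 6 and 8.

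**The concern.** Two problems arise whichever women are analysed. First, a raw coefficient is in MADRS points per assay unit, so its size against another assay's coefficient depends on the units chosen. Second, finding one coefficient large and the other small is not evidence that they differ. Two equal effects, each estimated imprecisely, often give one estimate that passes a threshold and one that does not.

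Two biases are also possible, because hormone levels on treatment are not randomised. If both arms are pooled without an arm term, a treatment effect by another route loads onto the hormone that better separates the arms. In any population, leaving out baseline MADRS can confound the coefficients if hormone levels relate to baseline severity.

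At stake is the mechanistic conclusion. The protocol's Background and Significance says that, if the preliminary findings are confirmed, the results would be the basis for a larger trial of a mood effect acting through neuroactive steroids.

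**Working it through.** The documents give no figure for Aim 1B to reproduce. The only input taken from them is 50 women per arm. Assumed: residual SD 8 MADRS points, two-sided p<0.05 in the benefit direction as the reading of *large*, and the correlations and effects below. Simulations used 20,000 trials per cell.

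**Units.** In one simulated data set with equal true effects, the standardised coefficients were -0.306 (free testosterone) and -0.313 (3alpha-diol). Changing units so that the free testosterone SD is 10 times larger gives raw coefficients of -0.031 and -0.313. Doing the same to 3alpha-diol gives -0.306 and -0.031. This affects a reading by size. A reading by p-value is free of units but meets the next problem.

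**Precision, 50 treated women, correlation r = 0.3.**
- SE of one coefficient: 8/√(n(1-r²)) = 8/√(50 × 0.91) = 1.19 points per SD (simulated 1.22).
- SE of the difference: 8 × √(2/(n(1-r))) = 8 × √(2/35) = 1.91 (simulated 1.97).
- With a true effect of 2 for each hormone, 2/1.22 = 1.64 against a critical value of about 2.01. Each hormone is then significant in roughly 36% of trials, so a split result is common.

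**Both hormones equally active at 1 / 2 / 3 points per SD: trials naming exactly one.**

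| Correlation | No stop | Stop at 0.6 | Stop at 0.5 |
|---|---|---|---|
| 0.3 | 23 / 53 / 50% | 23 / 53 / 50% | 21 / 50 / 47% |
| 0.6 | 19 / 50 / 67% | 10 / 25 / 30% | 3 / 8 / 9% |

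Reading *large* by size on a common scale (at least 2 against under 1 point per SD, r = 0.3) gives 23%, 26% or 10%. Requiring both the hormone's own 95% CI and the CI of the difference to exclude zero gives 4.5%, 5.0% or 5.1% at r = 0.3.

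**Pooled arms, no arm term.** Assume neither hormone is active, within-arm r = 0.3, and treatment shifts of 1 SD in free testosterone and 2 SD in 3alpha-diol.
- Pooled variances are 1 + 0.25 = 1.25 and 1 + 1 = 2. The covariance is 0.3 + 0.5 = 0.8, so the pooled correlation is 0.8/√2.5 = 0.51.
- A treatment effect of 4 points by another route gives expected coefficients of -4 × (2 × 0.25 - 0.8 × 0.5)/1.86 = -0.22 for free testosterone and -4 × (1.25 × 0.5 - 0.8 × 0.25)/1.86 = -0.91 for 3alpha-diol, where 1.86 = 1.25 × 2 - 0.8².
- With SE 0.67, 3alpha-diol alone is significant in 26% of trials (16.5% to 37.5% for effects of 3 to 5 points). A stop at 0.5 on the pooled correlation leaves 8% to 18%. With an arm term it is 4% to 5%.
- If free testosterone shifts more, the false verdict mostly goes to free testosterone.
- A 0.5 cut-off fires in about 56% of trials on the pooled correlation and about 1% on the within-arm one.

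**Baseline MADRS omitted.** Assume neither hormone is active, baseline-outcome correlation 0.5, 3alpha-diol correlated -0.2 or -0.3 with baseline MADRS, free testosterone not, and hormone correlation 0.3.
- The expected 3alpha-diol coefficient is -(0.2 × 0.5 × 8)/0.91 = -0.88, or -(0.3 × 0.5 × 8)/0.91 = -1.32 points per SD.
- 3alpha-diol alone is named in the benefit direction in about 10% to 20% of trials in 50 treated women, and about 15% to 34% in 100 women with an arm term. Adding baseline MADRS brings this to 2% to 3%.

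**The case against.** **The Aim 1 model might be meant.** Aim 1B belongs to Specific Aim 1, whose mixed model has a treatment effect and baseline MADRS. But the SAP says when that model is reused. For functional measures: "The same methods as described for MADRS score analyses will be used to analyze functional measures, including the SF-36". For Aim 3, the model applies "using methods and assumptions as in Specific Aim 1 Data Analysis, above". Aim 1B has no such statement and names linear regression instead. The Aim 1 secondary analyses of baseline hormones "and changes in the same variables over the 8-week period" overlap with it but supply none of the missing items.

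**The correlation safeguard.** This objection has force. 3alpha-diol is a metabolite of testosterone, and the SAP foresees a high correlation. At correlation 0.6 a cut-off of 0.5 removes most of the problem. At 0.3 it removes little. Without a cut-off, and without saying whether the correlation is pooled or within-arm, the protection is unknown.

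**The reading of *large*.** Reading it as p<0.05 is an assumption, as is any other reading. The SAP speaks of one hormone correlating with MADRS and the other not, which is close to it but not the same. The rates show direction and rough size only.

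**Pooling.** A reader might infer that the arms will be pooled and that 3alpha-diol will be falsely favoured. The documents do not support this. The population is not stated, the conversion and absorption wording may well mean treated women only, and the bias could favour either hormone.

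**Conclusion.** The concern holds as a defect in the decision rule. Its unit dependence, and the lack of any test that the coefficients differ, do not rest on assumed figures. The error rates do: in treated women with two equally active hormones they run from about 3% to 67%, depending on the correlation, the effect size, the cut-off and the reading of *large*. No single figure in that range is a property of the plan. The simulations also ignore the protocol's dose adjustment on free testosterone (Drug Safety), which may narrow its spread in treated women.

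The arm-term bias is conditional on pooling. The baseline-severity bias is possible in any population, so leaving out baseline MADRS is not merely a loss of precision. The protocol's Specific Aim 5 expects lower androgen and neuroactive steroid levels in postmenopausal women with treatment-resistant depression than in healthy controls. That makes a link with severity plausible, but does not show one among the randomised women.

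A reader might infer that the efficacy result is in doubt. It is not: this is a mechanistic sub-aim, and the Aim 1 treatment comparison does not use this regression. The SAP should be changed, because the rule can name a mechanism without evidence that the two hormones differ.

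**What to change.** Replace the rule in the Aim 1B paragraph with the following.

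- State the population.
- Regress week-8 MADRS on treatment arm, baseline MADRS, free testosterone and 3alpha-diol. Week 8 is the only on-treatment visit with the neuroactive panel.
- Divide each hormone by its pooled within-arm SD (the SD after removing arm means), and fix this scale in advance.
- Prefer one hormone only if its own 95% CI and the 95% CI of the difference both exclude zero. Otherwise report no determination.
- State the within-arm correlation above which no determination is made.
- Report an association rather than the active factor, because hormone levels are not randomised.
- Treat a repeat in the testosterone arm alone as supportive only. Its chance of naming 3alpha-diol, if only 3alpha-diol acts, is about 16% or 32% at 2 or 3 points per SD.

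This needs SAP wording only. Week-8 MADRS, free testosterone and the panel are already scheduled (3alpha-diol is assumed to be in the panel).

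The cost is precision and more inconclusive results. With the assumed 2 SD shift, the arm term raises the SE of the 3alpha-diol coefficient from about 0.67 to 0.86 points per SD. If only 3alpha-diol acts, the proposed rule names it in about 58% of trials at 3 points per SD, against 89% for significant-versus-not in the same model. At 2 points it is 29% against 61%.
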